15.0 STATISTICAL CONSIDERATIONS

15.1 Design and Sample Size

This is a multi-institutional, open-labeled, Phase II study. The study will be conducted at five institutions (including Washington University). Patients with previously treated, metastatic esophagogastric adenocarcinomas will be assigned to treatment with irinotecan plus ramucirumab.

Target sample size for this single arm, phase II study would be **40 patients**. A sample size of 40 has 85% power at a 0.050 significance level to detect a median progression-free survival time of 4 months in the treatment group when the median survival time of the

historic control group is 2.5 months. These estimations are based on historical data from irinotecan studies and a PFS improvement of 1.5 months seen in the RAINBOW study (PFS for paclitaxel alone = 2.9 months, paclitaxel plus ramucirumab = 4.4 months). Calculation is based on one-sided, one-sample log-rank test and assumes that subjects will be accrued for a period of 12 months, and follow-up continues for a period of 12 months after the last subject is enrolled.^{42,43} The survival time distributions of both groups are assumed to follow an exponential distribution.

15.2 Primary Efficacy Measure

Progression-Free Survival (PFS):

PFS will be measured from date of study entry to first radiographic progression or death due to any cause. Radiographic progressive disease (PD) will be defined using Response Evaluation Criteria in Solid Tumors v1.1 (RECIST v1.1).⁴¹ For those who are alive and do not experience progression, we censor them at the time of loss to follow-up (very few) or at 12 months from the study entry, which come first.

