5.6 Duration of Therapy

If at any time the constraints of this protocol are considered to be detrimental to the patient's health and/or the patient no longer wishes to continue protocol therapy, the protocol therapy should be discontinued and the reason(s) for discontinuation documented

Protocol Version: 10Jun2022 – Amendment 6 Page 20 of 64

in the case report forms.

In the absence of treatment delays due to adverse events, treatment may continue indefinitely or until one of the following criteria applies:

- Documented and confirmed disease progression
- Death
- Adverse event(s) that, in the judgment of the investigator, may cause severe or permanent harm or which rule out continuation of study drug, including:
 - o Grade 3 or 4 infusion reaction
 - o Grade 4 hypertension
 - o Grade 3 or 4 arterial thromboembolic event, or any PE/DVT occurring or worsening during anticoagulant therapy
 - One occurrence of urine protein level > 3 g/24 hours, three occurrences of urine protein level > 2 g/24, or urine protein level > 2 g/24 hours for more than 2 weeks
 - o Gastrointestinal perforation or fistula formation
 - o RPLS
 - Hepatic encephalopathy or other serious signs of liver impairment such as hepatorenal syndrome
- General or specific changes in the patient's condition render the patient unable to receive further treatment in the judgment of the investigator
- Suspected pregnancy
- Serious non-compliance with the study protocol
- Lost to follow-up
- Patient withdraws consent
- Investigator removes the patient from study
- The Siteman Cancer Center decides to close the study

Patients who prematurely discontinue treatment for any reason will be followed as indicated in the study calendar.

5.7 **Duration of Follow-up**

Patients will be followed every 2 months after discontinuation of treatment for progression and survival for 30 months. Patients removed from study for unacceptable adverse events will be followed until resolution or stabilization of the adverse event.

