10.0 STUDY CALENDAR

Screening/baseline evaluations are to be conducted within 28 days prior to start of protocol therapy. Cycles are 14 days long but may be extended to up to 21 days at physician discretion.

	Screening	Day 1 of each cycle (±/- 3 days)	Every 8 weeks (+/- 3 days	EOT (+/- 3 days)	F/U ¹
Informed consent	X				
Demographics and medical history	X				
ECOG PS, Vitals, weight	X	X			
Height	X			X	
Physical exam	X	X		X	X^5
EKG	X X				
CBC	X	X		X	
CMP	X	X		X	
PTT/INR	X				
Urinalysis or Urine Dipstick ⁶	X	X		X	
β-hCG ²	X				
Imaging ³ and RECIST 1.1 time point response	X		X	X^4	
Ramucirumab		X			
Irinotecan		X			
Tumor Biopsy (Wash U only)	X^7				
Blood for angiome profiling			nt on C1D1, C5D1, . C9D1	X	
Blood for cfDNA			nt on C1D1, C3D1, D1, and C9D1	X	
Collection of HER2 status	At some point during the study				
Adverse event assessment	X			X	X
Survival information					X

- 1. 30 days after EOT visit, then every 2 months. AEs only collected for 30 days after treatment discontinuation.
- 2. Women of childbearing potential only
- 3. Imaging (CT or MRI) will be performed every 8 weeks, +/- 7days, regardless of dosing/cycle delays up to 1 year. After 1 year, the imaging frequency is at the discretion of the treating physician. Information from lesion evaluation by imaging done as part of routine care will be collected until progressive disease has been objectively determined if the patient discontinued treatment due to any other reason than progressive disease.
- 4. EOT imaging not required if most recent scan has been performed within 21 days prior to EOT.
- 5. Physical exam will only be done if the follow-up visit involves an in-person office visit.
- 6. A urine dipstick may be performed in lieu of a full urinalysis, however, if the dipstick is abnormal, confirm urine protein with a full urinalysis. If urinalysis or dipstick shows protein ≥ 2+, a 24-hour urine collection must be collected.
- 7. If safe and feasible, biopsies are to be performed at least 7 days prior to the planned C1D1. See Section 9.1 for additional information.

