12.0 MEASUREMENT OF EFFECT

12.1 Antitumor Effect – Solid Tumors

For the purposes of this study, patients should be re-evaluated for response every 8 weeks regardless of dosing/cycle delays. In addition to a baseline scan, confirmatory scans should also be obtained not less than 4 weeks following initial documentation of objective response.

Page 40 of 64

Information from lesion evaluation by imaging done as part of routine care will be collected until progressive disease has been objectively determined if the patient discontinued treatment due to any other reason than progressive disease.

Response and progression will be evaluated in this study using the new international criteria proposed by the revised Response Evaluation Criteria in Solid Tumors (RECIST) guideline (version 1.1).⁴¹ Changes in the largest diameter (unidimensional measurement) of the tumor lesions and the shortest diameter in the case of malignant lymph nodes are used in the RECIST criteria.

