12.4.3 Evaluation of Best Overall Response

The best overall response is the best response recorded from the start of the treatment until disease progression/recurrence (taking as reference for progressive disease the smallest measurements recorded since the treatment started). The patient's best response assignment will depend on the achievement of both measurement and confirmation criteria.

For Patients with Measurable Disease (i.e., Target Disease)

For Tatients with Measurable Disease (i.e., Target Disease)				
Target	Non-Target	New	Overall	Best Overall Response
Lesions	Lesions	Lesions	Response	when Confirmation is
			_	Required*
CR	CR	No	CR	>4 wks. Confirmation**
CR	Non-CR/Non-	No	PR	
	PD			
CR	Not evaluated	No	PR	>4 wks. Confirmation**
PR	Non-CR/Non-	No	PR	24 wks. Commination .
	PD/not			
	evaluated			
SD	Non-CR/Non-	No	SD	Documented at least once
	PD/not			>4 wks. from baseline**
	evaluated			24 WKS. Holli baselille
PD	Any	Yes or	PD	
		No		
Any	PD***	Yes or	PD	no prior SD, PR or CR
		No		
Any	Any	Yes	PD	

^{*} See RECIST 1.1 manuscript for further details on what is evidence of a new lesion.

Note: Patients with a global deterioration of health status requiring discontinuation of treatment without objective evidence of disease progression at that time should be reported as "symptomatic deterioration." Every effort should be made to document the objective progression even after discontinuation of treatment.

^{**} Only for non-randomized trials with response as primary endpoint.

^{***} In exceptional circumstances, unequivocal progression in non-target lesions may be accepted as disease progression.

For Patients with Non-Measurable Disease (i.e., Non-Target Disease)

Non-Target Lesions	New Lesions	Overall Response
CR	No	CR
Non-CR/non-PD	No	Non-CR/non-PD*
Not all evaluated	No	not evaluated
Unequivocal PD	Yes or No	PD
Any	Yes	PD

^{* &#}x27;Non-CR/non-PD' is preferred over 'stable disease' for non-target disease since SD is increasingly used as an endpoint for assessment of efficacy in some trials so to assign this category when no lesions can be measured is not advised

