12.4.5 Progression-Free Survival

PFS is defined as the duration of time from start of treatment to time of progression or death, whichever occurs first. For those who are alive and do not experience progression, we censor them at the time of loss to follow-up (very few) or at 12 months from the study entry, which come first.

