15.3 Secondary Efficacy Measures

- Overall Survival Time (OS):
 - OS time will be measured from date of study entry to date of death from any cause. For those who are alive, we censor them at the time of loss to follow-up (very few) or at 30 months from the date of treatment discontinuation, which come first.
- Time to Progressive Disease (TTP):
 - TTP is defined as the time from study entry until date of radiographic PD using RECIST v1.1 criteria. For those who are alive and do not experience progression, we censor them at the time of loss to follow-up (very few) or at 12 months from the study entry, which come first. For those who are dead before progression, we will consider death as the competing risk. If the number of death are very small, we will censor them at time of death.
- Best Overall Response (BOR) of Complete Response (CR), Partial Response (PR), Stable Disease (SD) or PD:
 - BOR is defined as the best response across all time points from randomization until radiologically confirmed PD using RECIST, v1.1 criteria. CR is defined as the disappearance of all target and non-target lesions and any pathological lymph nodes (whether target or non-target) must have reduction in short axis to <10 mm and normalization of tumor marker level of non-target lesions. PR is defined as having a \geq 30% decrease in sum of longest diameter (LD) of target lesions. PD was defined as having a \geq 20% increase in sum of LD of target lesions and \geq 5 mm increase above nadir. SD was defined as small changes that did not meet above criteria.
- Objective Response Rate (ORR):
 ORR is defined as the percentage of participants with confirmed CR or confirmed PR.
- Clinical Benefit Rate (CBR):
 CBR is defined as percentage of combined patients who have achieved confirmed CR,
 PR and SD.

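### PFS and TTP are censored at loss of contact or month 12, not at the last tumour assessment; the direction of any bias depends on survival figures that the plan does not give

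*Combined protocol and SAP*

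**What the plan says.** - **PFS.** An event is radiographic progression or death (15.2). Otherwise, "we censor them at the time of loss to follow-up (very few) or at 12 months from the study entry, which come first". Section 12.4.5 has the same rule.
- **TTP (15.3).** The same censoring rule applies. Death before progression is a competing risk, or is censored if such deaths are very few.
- **OS (15.3).** The same phrase is used: "For those who are alive, we censor them at the time of loss to follow-up (very few) or at 30 months from the date" on which therapy stopped.
- **Contact after stopping (5.7).** "Patients will be followed every 2 months after discontinuation of treatment for progression and survival for 30 months".
- **Imaging after stopping (Section 10, footnote 3; repeated in 12.1).** "Information from lesion evaluation by imaging done as part of routine care will be collected until progressive disease has been objectively determined". This covers those who stopped for reasons other than progression. The calendar marks survival information, but no imaging, in its follow-up column.
- **End-of-treatment scan (Section 10, footnote 4).** "EOT imaging not required if most recent scan has been performed within 21 days prior to EOT".
- **A group the plan itself names (12.4.3).** "Patients with a global deterioration of health status requiring discontinuation of treatment without objective evidence of disease progression at that time" are recorded as symptomatic deterioration, and sites are asked to try hard to document progression afterwards.

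No section defines loss to follow-up, or says how missed scans or new anticancer therapy affect the censoring date.

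**The concern.** Progression can be seen only on a scan, but the censoring date is tied to contact. For OS, loss to follow-up can only mean loss of contact, and the PFS and TTP rules use the same words. A patient who stops without progression, is not scanned again and still answers the two-monthly contact is therefore not lost. That patient stays in the risk set as progression-free until death or month 12.

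The trial has one arm, so no control group shares this effect. The primary test compares observed events with the number expected under a fixed 2.5-month median. Unscanned time adds to the expected count, while death is the only event that can be observed against it. At stake are the type I error of the primary test and the accuracy of the PFS and TTP estimates. For TTP only the estimate is affected, since no TTP test is specified.

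**Working it through.** **1. The plan's own figure.** Inputs from 15.1: n = 40, one-sided 0.05, null median 2.5 months, alternative 4 months, exponential, 12 months' accrual plus 12 months' follow-up. The one-sample log-rank formula gives n = 38.98 and power 85.7% at n = 40. With every patient capped at month 12:

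- Event probability: 1 - 0.5^(12/4) = 0.875.
- Null-expected events per patient under the alternative: (4/2.5) x 0.875 = 1.4; difference 1.4 - 0.875 = 0.525.
- Variances per patient: 1.4 (null) and 1.780 (exact, under the alternative).
- Power: Phi[(sqrt(40) x 0.525 - 1.645 x sqrt(1.4)) / sqrt(1.780)] = Phi(1.03) = 84.8%.

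Both agree with the stated 85%. The calculation models no missed scans.

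**2. One unscanned patient.** The null hazard is ln2/2.5 = 0.28 expected events per month. Suppose the last scan is at s months and survival after it is exponential with median m. From s to month 12:

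- O = 1 - 0.5^((12 - s)/m)
- E = O x m/2.5
- O - E = O x (1 - m/2.5)

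The sign depends only on whether m is above or below 2.5. Under the null, 40 patients have E = 40 x (1 - 0.5^(12/2.5)) = 38.6, so dividing by sqrt(38.6) = 6.2 gives the approximate shift in Z = (O - E)/sqrt(E). For s = 1.84 months (8 weeks):

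| m (months) | O | E | O - E | Shift in Z |
|---|---|---|---|---|
| 2 | 0.97 | 0.78 | +0.19 | +0.03 |
| 2.5 | 0.94 | 0.94 | 0 | 0 |
| 3 | 0.90 | 1.08 | -0.18 | -0.03 |
| 3.5 | 0.87 | 1.21 | -0.35 | -0.06 |
| 5 | 0.76 | 1.51 | -0.76 | -0.12 |

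For s = 3.68 months (16 weeks), O - E is -0.32 at m = 3.5 and -0.68 at m = 5.

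**3. What the documents say about m.** They give no direct figure. Two rough anchors come from subtracting medians:

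- Second-line chemotherapy: survival under 6 months (1.1) minus the 2.5-month null gives under 3.5 months.
- Paclitaxel plus ramucirumab: survival above 9 months (1.3) minus PFS of 4.4 months (15.1) gives about 4.6 months.

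**4. Size of the written rule.** Simulated trials of 40 patients, rejecting when Z < -1.645, with a 12-month cap. Unscanned patients are drawn from those progression-free at the first or second 8-week scan. Two models were used:

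- *Model A*: progression is found at the next 8-week scan, and 15% of events are deaths seen exactly. The true median is set to 2.02 months so that full scanning gives a size of 0.039. At a true 2.5 months the scan grid alone raises the size, which is a separate matter.
- *Model B*: progression is seen exactly and the true median is 2.5 months. Full scanning again gives 0.039.

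Ranges across both models:

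| Median survival after stop | 2% unscanned | 5% | 10% |
|---|---|---|---|
| 2 months | 0.035-0.038 | 0.031-0.034 | 0.025-0.029 |
| 2.5 months | about 0.04 | about 0.04 | about 0.04 |
| 3 months | 0.043-0.044 | 0.044-0.050 | 0.052-0.058 |
| 3.5 months | 0.044-0.046 | 0.052-0.055 | 0.067-0.074 |
| 5 months | 0.050-0.054 | 0.068-0.079 | 0.11-0.13 |

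Of 40 patients, 5% is 2 and 10% is 4. These shares of all patients are about 10-12% and 21-25% of those progression-free at the stop. The shares and the survival values are assumptions.

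**The case against.** **The exposed group is small.** An affected patient must stop without progression, show none on the end-of-treatment scan, have no routine scan afterwards, stay in contact and not die soon. Follow-up is for progression as well as survival, and 12.4.3 asks for effort to document progression. This stands. No document supports 5% or 10%, and a single such patient leaves the size at 0.044-0.053 even with 3.5 to 5 months' survival.

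**The plan may already require the scans.** The first sentence of footnote 3, on 8-weekly imaging up to 1 year, could be read to cover patients off treatment. But the same footnote then covers those who stopped without progression through routine-care imaging, and the follow-up column has no scan.

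**Loss to follow-up could be read by endpoint**, as loss of progression follow-up for PFS and TTP. The term is undefined, so this is possible. The shared wording for OS points the other way, and even this reading gives no censoring date.

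**A reader might infer that the rule inflates type I error.** The documents do not support that. Survival of about 4.6 months comes from an effective regimen, whereas type I error is judged under the null. The chemotherapy anchor is only an upper limit of 3.5 months and allows values at or below 2.5. Patients who stop for global deterioration may well survive for less time than others. The direction is unknown.

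**Last-scan censoring is not free.** Keeping late deaths while dropping survivors' unscanned time makes the test conservative. At 2% unscanned and 3.5 to 5 months' survival, the written rule (0.044-0.054) lies closer to 0.05 than the replacement does (0.031-0.039). This stands and belongs with the recommendation.

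**Conclusion.** The point holds as a defect in the stated rule: as written, in-contact but unscanned patients count as progression-free until death or month 12. The size of the effect is not known. Over 2-10% unscanned and 2 to 5 months' median survival after the stop, the simulated one-sided size runs from 0.025 to 0.13, against about 0.04 with full scanning. At 3 months or less it stays between 0.025 and 0.058. Excess size is possible, not established, and below 2.5 months the rule works against the treatment.

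These figures assume exponential survival after the stop, stops at the first or second scan, and stopping that is random among progression-free patients. The planned 40 patients and 85% power are not in question. Severity is minor to should-fix: probably few patients are affected, but the wording is easily repaired before the analysis.

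**What to change.** In 12.4.5, 15.2 and the TTP text of 15.3, state: *Patients alive without documented progression are censored at the last evaluable tumour assessment (including the end-of-treatment scan) on or before month 12, or at time zero if there is no post-baseline assessment.* Time zero should be one date: 12.4.5 counts from start of treatment and 15.2 from study entry.

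- For PFS, deaths on or before month 12 remain events at the date of death, including those after missed scans. Leave the TTP rule for deaths unchanged.
- Report the number of patients censored with a scan gap.
- Sensitivity analysis 1: the currently written rule.
- Sensitivity analysis 2: symptomatic deterioration or start of new anticancer therapy counted as an event, because last-scan censoring can be informative.

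**Cost.** Wording, two analyses and one count; no new scans or patients. The Follow Up Form (Section 11) must capture the start date of new anticancer therapy if it does not already. The test becomes conservative: size about 0.015-0.04 over 0-10% unscanned and 2 to 5 months' survival. Power is about 84-87% with nobody unscanned, 78-86% at 5% and 73-84% at 10%, against 86-87% under the written rule with full scanning.

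### The month-12 censoring point for PFS and TTP covers only event-free patients, so whether time after month 12 counts depends on the outcome

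*Combined protocol and SAP*

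**What the plan says.** Section 15.2 defines PFS as time from study entry to first radiographic progression or death from any cause, with no upper time limit on either event. For patients alive without progression, "we censor them at the time of loss to follow-up (very few) or at 12 months from the study entry, which come first". Section 12.4.5 has the same rule, limited to the same patients: "For those who are alive and do not experience progression, we censor them at the time of loss to follow-up (very few"). The TTP paragraph of 15.3 repeats it and treats death before progression as a competing risk.

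Three places allow progression to be observed after month 12:

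- Section 15.1, on the design: "follow-up continues for a period of 12 months after the last subject is enrolled". With 12 months of accrual, that is 12 to 24 months per patient.
- Section 5.7: "Patients will be followed every 2 months after discontinuation of treatment for progression and survival for 30 months".
- Section 10.0, footnote 3: imaging is every 8 weeks up to 1 year, then at a frequency left to the treating physician.

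On size, section 15.1 states: "A sample size of 40 has 85% power at a 0.050 significance level". The stated aim is "to detect a median progression-free survival time of 4 months in the treatment group", where the median in the "historic control group is 2.5 months". On the method it says: "Calculation is based on one-sided, one-sample log-rank test", with exponential survival.

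No section says whether a progression or death after month 12 is counted or disregarded.

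**The concern.** A censoring time should not depend on what happens to the patient afterwards. Under the wording as it stands, it does. Two patients are both progression-free at month 12. One progresses at month 15 and contributes 15 months and an event. The other is still progression-free at month 20 and contributes 12 months.

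Two consequences follow. After month 12 the risk set holds only patients who go on to fail, so an estimated PFS curve falls too fast there. In the one-sample log-rank test, late events stay in the observed count O, while the event-free exposure beyond month 12 is removed from the expected count E. Both effects work against the regimen. At stake are the late part of the PFS curve and an unambiguous event count for the primary endpoint of a study that section 15.4 intends as groundwork for phase III.

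**Working it through.** **Inputs.** From 15.1: n = 40; medians 2.5 months (null) and 4 months (alternative); one-sided 5%; 12 months of accrual; 12 months of follow-up after the last patient; exponential survival. Assumed here: uniform accrual, no dropout, and exact observation of progression. The hazards are λ0 = ln 2/2.5 = 0.2773 and λ1 = ln 2/4 = 0.1733 per month, so the hazard ratio is 0.625.

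**Step 1: the plan's own figure.** For the one-sample log-rank test with per-patient expected events v0, observed events v1 and variance s² under the alternative,

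power = Φ{[(v0 − v1)√n − 1.645√v0] / s}.

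With 12 to 24 months of follow-up, v0 = 1.5158, v1 = 0.9474 and s² = 2.1623. This gives (0.5684 × 6.325 − 1.645 × 1.231)/1.470 = 1.07, so power is 85.7%, and 39 patients give 85%. The stated 85% is reproduced for follow-up without a month-12 cut.

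**Step 2: patients affected at a 4-month median.**

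- Event-free at month 12: 40 × 2^(−3) = 5.0.
- Event by the month-24 data cut: 40 × [1 − (0.125 − 0.0156)/(12 × 0.1733)] = 37.9.
- Event-free at the cut, so pulled back to month 12: 40 − 37.9 = 2.1.
- Late events counted after month 12: 5.0 − 2.1 = 2.9.
- Chance of at least one late event: 1 − (1 − 2.9/40)^40 = 95%. At a 2.5-month median there are 1.02 late events on average, and the chance is 64%.

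**Step 3: the log-rank test.** Under the rule as written, mean O stays at 37.9 while mean E falls from 60.6 to 58.3. That is 2.3/0.2773, about 8 patient-months of event-free exposure discarded. Simulation used 400,000 trials per scenario, Z = (E − O)/√E and critical value 1.645; repeat runs agreed within about 0.2 point.

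| Rule | Power, median 4 | Level, median 2.5 |
|---|---|---|
| As written | 85.2% | 2.95% |
| Everyone cut at month 12 | 87.3% | 4.0% |
| Everyone followed to the data cut | 88.5% | 3.95% |

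Simulated and formula power differ (88.5% and 85.7% for the same no-cut design), so compare rules only within one scale.

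**Step 4: the curve, if Kaplan-Meier is used.** With at least 12 months of follow-up for everyone, all event-free patients remain at risk to month 12 under every rule, so the estimate to that point is identical. Beyond it, at a 4-month median, the curve ends at zero in 95% of trials as written, against 45% with follow-up to the cut. Mean 18-month PFS:

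| True median (months) | As written | True value |
|---|---|---|
| 4 | 1.7% | 4.4% |
| 6 | 3.8% | 12.5% |
| 8 | 6.2% | 21.0% |

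**Step 5: dependence on the data cut.** If minimum follow-up is 24 months instead of 12, power is about 87.9% as written, 87.2% with everyone cut at month 12 and 89.1% with no cut.

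**The case against.** The strongest reply is that a common 12-month window was meant. Protocol-fixed imaging stops at 1 year, and the 30-month follow-up in 5.7 matches the OS censoring rule in 15.3. Under that reading there is no outcome-dependent censoring. This stands as a possible intent, but the text does not say it: the PFS event is uncapped, the cap is limited to event-free patients, and 5.7 names progression as well as survival. Two analysts could reach about 38 or 35 events from the same data. A common window would also depart from the 12 to 24 months of follow-up behind 15.1.

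Other points that stand: section 15 does not name Kaplan-Meier or set an 18-month PFS endpoint; it names the one-sample log-rank test only for the sample size; and at the design alternative the affected tail rests on about 5 of 40 patients.

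A reader might infer more than the documents support:

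- *That the primary test falls short of its planned power.* It does not. Power under the literal rule is still about 85%, and the loss is relative to consistent rules that do better. At true medians of 6 and 8 months, power exceeds 99.9% under all three rules.
- *That the rule could create a false positive.* It lowers the level.
- *That the median PFS is distorted.* A median before month 12 is unaffected.
- *That the curve must always reach zero.* It does so only when at least one late event is counted.

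**Conclusion.** The wording should be corrected. Taken literally, it is an outcome-dependent censoring rule on the primary endpoint. Its main cost is a downward bias in PFS beyond month 12, which grows with the benefit of the regimen: at 18 months, roughly a factor of 2.6 at a 4-month median (4.4/1.7) and 3.4 at 8 months (21.0/6.2). The cost to the test is about 2 to 3 points of simulated power and about 1 point of level, both in the conservative direction, with the stated 85% still met.

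These sizes rest on exponential PFS, uniform accrual, no dropout, complete observation of late progression and analysis at month 24. With longer follow-up the power loss against no cut shrinks to about 1 point. For TTP the same mismatch would affect the cumulative incidence of progression; that effect was not quantified.

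**What to change.** Use one horizon for events and non-events, in the same words in 12.4.5, 15.2 and the TTP paragraph of 15.3.

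- **Preferred, because it matches 15.1:** delete the month-12 cut and censor event-free patients at their last adequate tumour assessment on or before the data cut. About 37.9 events are expected, with formula power 85.7%. The downside is reliance on imaging that is discretionary after 1 year. Censoring at the last assessment also gives slightly less exposure than the formula assumes.
- **Alternative:** administratively censor every patient at 12 months, state that later progression or death is not counted, and restate 15.1 as 12 months of follow-up per patient. About 35 events are expected. With v0 = 1.400, v1 = 0.875 and s² = 1.7803, formula power is Φ(1.03) = 84.85%, marginally under the stated 85% (41 patients would be needed). This gives up about 3 late events. If minimum follow-up turned out to be 24 months, it would have slightly less power than the present wording (87.2% against 87.9%).

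Either way the cost is one sentence in three places, plus a restated 15.1 under the alternative. The shared sentence must also settle the time origin, since 12.4.5 starts PFS at the start of treatment and 15.2 at study entry.
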